7.1 Statistical analysis

We will compile an encrypted record of each patient and the study or control solution that was administered to each breast intraoperatively. We will then record data from the condition-specific physical examination at each post-operative clinic visit to track presence of hematoma, presence of seroma, laterality with worse bruising, amount of drain output prior to removal, and number of days with drain prior to removal.

Demographic and surgical details will be collected for each patient. These will include patient demographics (i.e., age, BMI, race, ethnicity), clinical cancer characteristics (i.e., type of cancer, neoadjuvant chemo or radiation, adjuvant chemo or radiation), and post-operative outcomes (i.e., hematoma, seroma, infection, return to the operating room, radiology aspiration or drain placement, clinic aspiration). Results will be analyzed comparing the outcomes of the TXA treated breasts with the Control (Saline) treated breasts using T test for continuous variables, and Chi Squared for categorical variables.

Multivariate regression analysis will also be utilized to assess for the importance of various clinical and demographic factors (BMI, cancer laterality, etc.) on overall outcomes. For ecchymosis, the prevalence of worse ecchymosis with or without TXA will be reported as rated by the provider and patient at post operative visits.

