1.2 Background on the Investigational Product(s) and Associated Known Toxicities

TXA is a synthetic amino acid that blocks plasminogen conversion to plasmin to stabilize clot formation [16]. Despite the fact that TXA is only FDA-approved for hemophilia patients to reduce hemorrhage and need for replacement therapy following tooth extraction [16], many high powered double-blind randomized trials have published their results using TXA in other surgical specialties. Prior orthopedic arthroplasty studies have shown that a single intraoperative dose of TXA prior to incision significantly decreases blood loss and transfusion requirements without associated thrombotic complications [6, 7, 11, 17]. These have shown that not only intravenous, but also directly infiltrating the joint topically can decrease bleeding [6, 12]. Furthermore, there have not been any report of increased systemic thrombosis when used topically. In plastic surgery, TXA is routinely dosed intravenously prior to incision for pediatric craniosynostosis cases to minimize blood loss, decrease transfusion requirements, and shorten length of hospital stay [3, 4, 9]. The literature also shows when used topically it can significantly decrease bruising and bleeding in rhinoplasty, rhytidectomy, and liposuction [8, 10, 18, 19].

More recently, there have been retrospective studies in breast plastic and oncologic surgery evaluating the use of TXA without any evidence of thrombotic complications. Weissler et al published a retrospective review of immediate post-mastectomy tissue

expander placement which showed a statistically significant decrease in hematoma with intravenous TXA administration[13]. Perhaps most pertinent for our study is the small trial from Ausen et al in the Netherlands in which they examined topical moistening of mastectomy flaps with a dilute TXA solution. They found no complications were related to topical administration of TXA relative to the control group[15]. This small study trended toward decreasing hematoma rates and drain volumes, and inspired our own study design of using each patient as their own internal control. We hope to build off this study given our large volume of mastectomies, and low risk profile of utilizing topical TXA. Additionally, designing the study such that each patient receives a control and experimental dose (saline on one side, TXA on the other) will help us to control for any confounding patient factors and further validate our results.

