3.2 Sample Size

The goal enrollment is 150 patients, 300 breasts. Given that the literature cites a hematoma rate of up to 5% in mastectomy patients, if we aim for complete reduction with TXA, we will need at least 150 per group to be adequately powered to detect that difference (alpha 0.05, beta 0.2). However, since complete reduction is not realistic, we will aim to recruit as many as possible but with a minimum goal of 150 patients (150 breasts will receive TXA, 150 breasts will receive saline).

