3.3.1 Inclusion Criteria

In order to be eligible to participate in this study, an individual must meet all of the following criteria:

1. Histologically confirmed breast malignancy OR increased risk for breast cancer

2. Age \geq 18 years
3. Scheduled to undergo bilateral mastectomy with plastic surgery closure or reconstruction
4. Ability to understand a written informed consent document, and the willingness to sign it
5. At least 4 weeks post-completion of chemotherapy or radiation therapy

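### Section 7.1 plans no within-patient TXA effect adjusted for cancer side, a factor that can differ between a patient's two breasts

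*Combined protocol and SAP*

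**What the plan says.** The main comparison is in Section 7.1: "Results will be analyzed comparing the outcomes of the TXA treated breasts with the Control (Saline) treated breasts", with a t test for continuous outcomes and chi-squared for categorical ones. Neither is described as paired, and neither has a covariate.

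The same section then adds a multivariate regression to gauge how much clinical and demographic factors matter: "BMI, cancer laterality, etc.) on overall outcomes". Treatment is not named as a term in that model, nor is the pairing of breasts within a patient. No adjusted TXA effect is promised from it.

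Section 1.2 relies on the split-body design, which "will help us to control for any confounding patient factors and further validate our results". Eligibility in Section 3.3.1 is "Histologically confirmed breast malignancy OR increased risk for breast cancer", with all patients having bilateral mastectomy. A patient may therefore have cancer in one breast, both or neither.

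On which breast receives TXA, the intraoperative text of Section 6.3 says the right. The calendar in Section 6.1, as extracted, has its mark on the left-breast row. Sections 3.1 and 5.1, and an earlier paragraph of Section 6.3, say only that one pocket is treated. No section describes randomising the side or balancing it by cancer side.

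**The concern.** Using each patient as her own control cancels what her two breasts share, such as age, BMI and race. It does not cancel what differs between them. In unilateral cancer one breast is the cancer side and the other is not, and the plan itself treats cancer laterality as a possible influence on outcomes. It nevertheless lists that factor with BMI, although BMI is the same for both breasts and cannot confound a within-patient contrast, while cancer side can.

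Two things are at stake. If cancer side affects drain output or duration, leaving it out adds spread to every within-patient difference. If TXA also falls on the cancer side in more or fewer than half of the unilateral cancers, part of the cancer-side effect is carried into the TXA estimate. It flatters TXA in one direction and masks a benefit in the other.

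**Working it through.** **The plan's own figure.** Section 3.2 states that "the literature cites a hematoma rate of up to 5% in mastectomy patients" and "if we aim for complete reduction with TXA, we will need at least 150 per group" ("alpha 0.05, beta 0.2"). For 5% versus 0%, two-sided, with unpooled variance: n = (1.960 + 0.842)² × 0.05 × 0.95 / 0.05² = 149.1, so 150 per group. With pooled variance it is 152, and power at 150 is 79.5%. The figure reproduces. The checks below use 150 pairs ("150 breasts will receive TXA, 150 breasts will receive saline").

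**Inputs the documents do not give (assumptions).**
- u, share of patients with unilateral cancer: 0.7.
- g, cancer-side shift in units of the residual SD of the paired difference: 0.3 to 0.5.
- f, share of unilateral cancers with TXA on the cancer side: 0.5, 0.6 or 0.7. The values 0.4 and 0.3 mirror the last two with the sign reversed.
- ρ, within-patient correlation: 0.5 unless stated. At this value the residual SD of the difference equals the SD of a single breast.

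**Model.** D = τ + g·c + e, where D is TXA minus saline, e has SD 1, and c is +1 if TXA is on the cancer side, −1 if on the other side, and 0 if cancer is bilateral or absent.

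**Precision, continuous drain outcomes.** Variance without adjustment divided by variance with it, at f = 0.5, is 1 + u·g².
- g = 0.3: 1 + 0.7 × 0.09 = 1.063. On 150 patients, 0.063 × 150 is about 9 more.
- g = 0.5: 1 + 0.7 × 0.25 = 1.175. On 150 patients, 0.175 × 150 is about 26 more.

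**Precision, hematoma.** With a rate of p = 5% and a cancer-side difference of d = 3 to 5 percentage points (assumed), the share of variance explained is u·d² / [2p(1−p)].
- d = 0.03: 0.00063 / 0.095 = 0.7%.
- d = 0.05: 0.00175 / 0.095 = 1.8%.

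**Shift in the estimate from an uneven split**, u(2f−1)g.
- f = 0.6: 0.7 × 0.2 × 0.3 = 0.042, and 0.7 × 0.2 × 0.5 = 0.070.
- f = 0.5: zero.
- Hematoma at f = 0.6: 0.7 × 0.2 × 3 = 0.42 to 0.7 × 0.2 × 5 = 0.70 percentage points, against the 5 points used for sizing.

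**False-positive rate at a given split, no true TXA effect, nominal 5% two-sided, ρ = 0.5.** The lower figure is for g = 0.3 and the upper for g = 0.5.

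| Split on cancer side | Paired test | Unpaired t test |
|---|---|---|
| 50/50 | 5% | 0.7% to 0.8% |
| 40/60 | 7.9% to 12.4% | 1.4% to 3.3% |
| 30/70 | 17% to 36% | 4.2% to 14.4% |

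The unpaired test is conservative here because its standard error ignores the positive correlation. At 40/60 it gives 4.5% to 8.5% if ρ is 0.25 and 8.2% to 13.5% if ρ is 0.

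**Chance splits.** With 0.7 × 150 = 105 unilateral cancers and a side unrelated to cancer, the 95% range for f is 0.40 to 0.60. A split of 40/60 or worse occurs in about 5% of trials.

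**The case against.** **The plan does not ignore cancer side.** Section 7.1 names cancer laterality in its regression. That stands, and the criticism is narrower: the regression is not specified so as to give a paired, adjusted TXA effect.

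**A reader might infer that the planned test has a false-positive rate of 8% to 12%.** The documents do not support this. The figure needs a paired test and an assumed 40/60 split. Section 7.1 does not say the t test is paired, and an unpaired test at correlation 0.5 stays below 5% at that split. The shift in the estimate is the same either way. Ignoring the pairing is a separate problem.

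**A reader might also infer that an uneven split is likely.** No section links the TXA side to the cancer side, and none gives a split. If the two are unrelated and cancers fall evenly left and right, the split averages out over repeated trials and a paired unadjusted test keeps its 5%. Systematic bias needs a side choice related to cancer, or unevenly distributed cancers, and the documents show neither. What stands is that they also describe nothing to prevent it.

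**The premise is not documented.** No section says that cancer side changes drain output or seroma. The plan only lists it as a factor worth examining.

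**The main outcome is barely touched.** Section 3.1 makes hematoma primary, and there the gain is under 2%. This also stands. The gain concerns drain output and duration, which are secondary.

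**The variable may not be collected.** The list of cancer characteristics in Section 7.1 gives type and treatment, not side. Collection is implied only by the regression sentence.

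**Conclusion.** The concern holds in a limited form. The TXA-saline comparisons are unadjusted, and the one model that mentions cancer laterality is not set up to estimate a within-patient TXA effect. The self-control design does not cover this factor in unilateral cancer.

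The firmest benefit is precision for the continuous drain outcomes, where adjustment removes variance inflation of about 6% to 18%. For hematoma the gain is negligible. Protection against an uneven split is worth 0.04 to 0.07 SD at 40/60 and nothing at 50/50. All of this rests on the assumed 70% unilateral share and the 0.3 to 0.5 SD shift; true size and direction are unknown. The documents do not support a stated false-positive rate for the planned test, or a claim that imbalance is probable. This is an inexpensive improvement to the analysis plan and does not invalidate the trial.

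**What to change.** In Section 7.1:

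1. Make the main analysis of drain output and of drain duration a regression of the within-patient difference (TXA minus saline) on one term, coded +1 if TXA was on the cancer side, −1 if on the other side, and 0 if cancer is bilateral or absent. The intercept is the TXA effect.
2. For seroma, use a conditional logistic model with treatment and a breast-level indicator of cancer. The within-pair difference of that indicator is the same +1/−1/0 term. A per-patient value entered directly would be constant within the pair and drop out.
3. Report the unadjusted result beside each adjusted one, and report how often TXA fell on the cancer side.
4. Name the side of cancer in the data-collection list.

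Separately, reconcile Sections 3.1, 5.1, 6.1 and 6.3 on which breast receives TXA. If TXA is always on the same side, adjusting for cancer side does not remove a plain right-left difference.

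The cost is a few lines of text, one degree of freedom and one listed data item. Fixing the term in advance also avoids a choice of adjustment after the data are seen.

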2.2 Primary Objective and Endpoint(s)

The primary objective of this study is to evaluate the impact of topical TXA versus control (saline) on key post-operative outcome measures. These include hematoma, seroma, drain output, drain duration, bruising, and reoperation.

Primary Objective	Endpoint(s)	Time Frame
1. To evaluate the impact of TXA on hematoma rates compared to control	Presence of hematoma in 30 day period	From application in the operating room to 30 days of follow up
2. To evaluate the impact of TXA on seroma rates compared to control	Presence of seroma in 3 month period	From application in the operating room to 3 months of follow up

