2.3 Secondary Objective(s) and Endpoint(s)

[figure not shown]
Secondary Objective	Endpoint(s)	Time Frame
1. To evaluate the impact of TXA on patient and provider rating of bruising, comparing the TXA side to the control side	
Ecchymosis will be compared between the right and left side at each post operative visit and documented. The observer will be blinded to the laterality of TXA	From application in the operating room to 30 days of follow up
2. To evaluate the impact of TXA on total drain output in the first post operative day	
Total drain output over the life of the drain, compared between control and study groups	From drain placement in the operating room to discharge on POD1
3. To evaluate the impact of TXA on total drain duration	
Total drain duration compared between control and study groups	From drain placement in the operating room to removal of the drain

3 Study Design

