3.1 Characteristics

We propose a prospective, placebo-control trial looking at the effect of topical tranexamic acid on post-operative bleeding, hematoma, seroma, drain output, and bruising in post-mastectomy breast reconstruction. We will recruit patients undergoing bilateral mastectomy at our institution. Patients will be excluded if they have previous history of bleeding or coagulation disorders. Each patient will serve as their own internal control, with one side receiving saline and the other TXA. During surgery and prior to wound closure, we will moisten the wound surface of one side with 20 cc of dilute TXA 25mg/ml solution, and the contralateral with 20cc of saline. Demographics, cancer details, and surgical characteristics will be collected. Outcomes will we assess include hematoma, seroma, reoperation, drain duration, and degree of ecchymosis will be recorded post-operatively for analysis over a 3-month period. The primary outcome will

be presence of hematoma. Secondary outcomes will include seroma, drain output and duration, ecchymosis, and return to operating room.

The surgeon will mix the TXA solution and pass onto the surgical field (detailed in a later section). After completion of the bilateral mastectomy, the plastic surgeon will perform their portion of the procedure. Immediately prior to final closure, 20ml of 25mg/ml TXA solution will be infiltrated into one breast pocket. 20ml of 0.9% normal saline will be infiltrated into the other breast pocket. No other hemostatic agents will be used. The sidedness of the TXA administration will be documented by the surgery team in our record but kept confidential from the surgery clinic staff to prevent bias at post-operative assessments. The solutions will be allowed to dwell while performing incisional closure, and the solutions will be evacuated by the Jackson-Pratt drain when placed to bulb suction at the end of the case. Post-procedure, each patient will be provided with standard post-operative instructions. They will be followed post-operatively for up to 1 year.

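### Section 7.1 does not say that the TXA-saline comparison is paired; run unpaired, it loses precision whenever a patient's two sides are positively correlated, except for hematoma at the planned 5% v 0%

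*Combined protocol and SAP*

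**What the plan says.** The design is within-patient. Section 3.1: "Each patient will serve as their own internal control, with one side receiving saline and the other TXA". Section 1.2 gives the reason: the arrangement "will help us to control for any confounding patient factors".

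The only analysis text is section 7.1. It compares TXA breasts with saline breasts "using T test for continuous variables, and Chi Squared for categorical variables". It then adds: "Multivariate regression analysis will also be utilized to assess for the importance of various clinical and demographic factors". Neither sentence mentions pairing, and the regression sentence gives neither the unit of analysis nor the handling of two breasts from one patient. A paired t test, McNemar, a mixed model, GEE and clustering are mentioned nowhere in the documents.

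The outcomes concerned are:
- Hematoma: in the primary table of section 2.2, and the single primary outcome in section 3.1.
- Seroma: in the primary table of section 2.2 ("To evaluate the impact of TXA on seroma rates compared to control"), but secondary in section 3.1.
- Drain output and drain duration: secondary in section 2.3, for example "Total drain duration compared between control and study groups".
- Bruising: already a within-patient comparison in section 2.3 ("Ecchymosis will be compared between the right and left side at each post operative visit and documented"). Section 7.1 plans only to report which side is worse.

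Section 3.2 sizes the trial on hematoma, 5% v 0%: "we will need at least 150 per group to be adequately powered to detect that difference".

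**The concern.** With one breast of each kind per patient, the data are 150 matched pairs. A test for independent groups uses a variance that ignores the covariance between the two sides. Body habitus, surgical technique and healing are shared by both sides, so a positive correlation is plausible. The unpaired standard error is then too large, and the trial gives up the precision for which section 1.2 chose the design.

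Regression can err in the opposite direction. If each breast is a row and clustering is ignored, a patient-level factor such as BMI is counted as if it came from 300 independent units, and its standard error is too small.

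Leaving the test open also allows it to be chosen after the data are seen. At 4 v 0 hematomas, chi-squared gives p = 0.044 and uncorrected McNemar 0.046, while mid-P McNemar gives 0.063 and exact McNemar 0.125.

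**Working it through.** **Inputs.** From the documents: 150 pairs; hematoma 5% v 0%; alpha 0.05 (taken as two-sided); power 80%. Assumed, because the documents give none: between-side correlation ρ, a drain effect of 0.25 SD, seroma 15% v 8%, and partial-reduction hematoma rates.

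**1. The plan's 150 per group.**
- Independent, pooled: [1.96√(2×0.025×0.975) + 0.8416√(0.05×0.95)]² / 0.05² = 151.9.
- Independent, unpooled: (1.96 + 0.8416)² × 0.0475 / 0.0025 = 149.1.
- Paired Wald: the variance of the difference is 0.05 − 0.05² = 0.0475, so again 149.1.
- McNemar: [1.96√0.05 + 0.8416√0.0475]² / 0.0025 = 154.6.

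The figure of 150 is reproduced under either reading, so it does not show which was meant.

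**2. Drain output and duration.** The unpaired variance is 2σ²/n and the true variance is 2σ²(1−ρ)/n, so the unpaired interval is 1/√(1−ρ) times as wide as it need be. The excess is 5/12/20/41/83% at ρ = 0.1/0.2/0.3/0.5/0.7. For power at 0.25 SD, 0.25/√(2/150) = 2.165:
- Unpaired, Φ[(2.165 − 1.96)/√(1−ρ)]: 58.1, 59.7 and 61.4% at ρ = 0, 0.3 and 0.5.
- Paired, Φ[2.165/√(1−ρ) − 1.96]: 58.1, 73.5 and 86.5%.

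**3. Seroma and hematoma.** The probability that both sides have the event is p₁p₂ + ρ√[p₁(1−p₁)p₂(1−p₂)]. For 5% v 2.5% at ρ = 0.3 this is 0.00125 + 0.3 × 0.0340 = 0.0115. With 150 pairs (McNemar by enumeration, chi-squared by simulation):

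| Setting | ρ | Chi-squared | Uncorrected McNemar |
|---|---|---|---|
| Seroma 15% v 8% | 0 | 48% | 48% |
| | 0.2 | 48% | 58% |
| | 0.3 | 48% | 64% |
| | 0.5 | 47% | 78% |
| Hematoma 5% v 2.5% | 0 | 20% | 19% |
| | 0.3 | 15% | 25% |
| | 0.5 | 11% | 34% |
| Null, 5% v 5% (error rate) | 0.3 | 1.9% | 4.3% |

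**4. Hematoma at 5% v 0%.** No patient can have hematomas on both sides, so the covariance is zero and pairing changes nothing. Chi-squared and uncorrected McNemar both reject from 4 v 0, mid-P from 5 v 0 and exact from 6 v 0. For X ~ Binomial(150, 0.05), P(X ≥ 4), P(X ≥ 5) and P(X ≥ 6) are 94.5, 87.4 and 76.6%. The choice here is between large-sample and exact tests.

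**5. Regression.** For a patient-level factor in a breast-level linear model without clustering, the true standard error is √(1+ρ) times the reported one. The error rate is 2[1 − Φ(1.96/√(1+ρ))] = 6.2/7.4/8.6/11.0% at residual ρ = 0.1/0.2/0.3/0.5.

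**The case against.** The strongest reply is that nothing here is shown to be wrong. A t test may be a paired t test, and chi-squared does not exclude McNemar. The protocol stresses the own-control design, section 6.3 has drain output charted by side, and section 7.1 keeps a record of which solution each breast received. Every loss is conditional on the tests being run unpaired, and its size rests on assumed inputs. This stands: the defect is an unstated method, and no particular loss is established.

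A reader might infer from the 150 per group that an independent-group analysis was planned. Step 1 shows that it fits both readings.

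A reader might also infer that ignoring the pairing inflates false positives for TXA v saline. With positive correlation it does the reverse, so validity is not threatened.

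The regression figures are likewise conditional. No unit of analysis is stated, one row per patient would not have the problem, and 6-11% is a linear-model result that does not carry over directly to a binary outcome.

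Finally, section 7.1 plans only descriptive reporting of bruising, so the absence of a test there is not a defect. Return to the operating room can be paired only if it is recorded by side, which the documents do not establish.

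**Conclusion.** The point holds as an unstated pairing that should be settled before analysis. If the tests are run unpaired with positively correlated sides, the treatment comparison is conservative. Drain output, drain duration and seroma lose precision by the amounts above, and nothing is lost at ρ = 0.

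It is tempting to say that hematoma is unaffected. That is true only at 5% v 0% or at ρ = 0, and section 3.2 itself calls complete reduction unrealistic. It is equally tempting to say that pairing would rescue the primary outcome. It would not: at 5% v 2.5% and ρ = 0.3, power rises from 15% to only 25%.

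The direction of these results follows from the design and a positive correlation. The sizes rest on assumed correlations, effects and event rates. The regression point applies only if a breast-level model without clustering is fitted.

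**What to change.** Reword section 7.1 so that TXA and saline breasts are compared within patient:

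1. Drain output and duration: paired t test on each patient's TXA-minus-saline difference.
2. Hematoma and seroma: one McNemar version, named before analysis, with a paired risk difference and 95% CI. Return to the operating room likewise, but only if it is recorded by side.
3. Any breast-level regression: clustering by patient (GEE or a random effect), with the unit of analysis stated.

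A sign test for the worse-bruised side is optional.

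The cost is wording; data, patients and visits are unchanged. The choice of McNemar version has a price at hematoma 5% v 0%:
- Uncorrected keeps 94.5% power, but by rejecting from 4 v 0, where the exact p is 0.125. Its null error reached at most 5.3% over rates of 2-20% and ρ from 0 to 0.5. At ρ = 0 it loses at most about 1 point of power to chi-squared in the settings computed.
- Mid-P gives 87.4% (94.5 − 87.4 = 7.1 points lower), with null error at most 4.9%.
- Exact gives 76.6% (17.9 points lower), with null error at most 3.7%.

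A separate matter: the study calendar in section 6.1 and the operative text in section 6.3 disagree on which side receives TXA, and those passages must be reconciled.

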The Impact of Topical Tranexamic Acid in Breast Reconstruction

Protocol Number: CC # 228012

Investigational Product(s): Topical Tranexamic Acid

Version Number: v4

Version Date: 1/26/24

[figure not shown]
IND Number: N/A

NCT Number: 05807074

Principal Investigator (Sponsor-Investigator)

[name]

University of California, San Francisco

Statistician

[name]

UCSF Surgery Biostatistics Core

Revision History

Version 2 08/12/2022

Version 3 09/27/2022

Protocol Signature Page

1. I agree to follow this protocol version as approved by the UCSF Protocol Review and Monitoring Committee (PRMC), Institutional Review Board (IRB), and Data and Safety Monitoring Committee (DSMC).
2. I will conduct the study in accordance with the International Council for Harmonisation of Technical Requirements for Pharmaceuticals for Human Use (ICH) Good Clinical Practices (GCP) and the applicable IRB, ethical, federal, state, and local regulatory requirements.
3. I certify that I, and the study staff, have received the required training to conduct this research protocol.
4. I agree to maintain adequate and accurate records in accordance with IRB policies, federal, state and local laws and regulations.

UCSF Principal Investigator

[name]

Printed Name

DocuSigned by:

A redacted signature field, indicated by a black rectangular box with a blue border.

Signature

1/26/2024

Date

Abstract

Title	The impact of topical Tranexamic Acid in reconstructive post-oncologic breast surgery
Study Description	Improvement in bleeding and bruising has been described by using both intravenous and topical off-label applications of Tranexamic Acid (TXA) in many surgical fields. The proposed prospective study will evaluate the utility of topical tranexamic acid in decreasing hematoma and seroma rates, drain output, and ecchymosis in post-mastectomy breast reconstruction patients. This novel use of TXA in breast surgery may provide a simple, cost-effective, and safe way to improve outcomes and satisfaction for our breast cancer patients.
Phase of Study	Phase 2
Investigational Products	Tranexamic Acid (Topical application)
Study population	Female patients > 18 years old undergoing bilateral mastectomy with reconstruction or complex closure
Primary Objective	To investigate whether topical tranexamic acid may impact rates of seroma, hematoma, severe bruising, and drain output in the post-mastectomy reconstructive population

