2.1 Hypothesis

Given the use of topical tranexamic acid in reducing bleeding and bruising in other surgical specialties, we believe that topical tranexamic acid can improve post-operative outcomes after breast cancer surgery in a cost-effective manner. We hypothesize that the use of topical TXA in the breast pocket prior to closure will lead to a significantly lower rate of breast hematoma or seroma requiring intervention, decrease overall drain output, and decrease subjective bruising when compared to the control breasts.

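### Section 7.1 gives bruising either no test or a two-group chi-squared on mutually exclusive counts, whose 5% test has a true size of 16.5% with no ties, 9.0% at 50% ties and 5.4% at 90% (tie share assumed)

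*Combined protocol and SAP*

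**What the plan says.** Section 7.1 lists what is recorded at each post-operative visit. For bruising the item is "laterality with worse bruising", which is one value per patient and visit, not a value per breast. Section 2.3 agrees: it sets the right side against the left at each visit, over 30 days, with an observer blinded to the TXA side.

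The comparative rule in Section 7.1 sets TXA breasts against saline breasts "using T test for continuous variables, and Chi Squared for categorical variables". No paired or one-sample method is named in the document, although each patient is her own control (Section 3.1). A later sentence in Section 7.1 deals with ecchymosis alone: "the prevalence of worse ecchymosis with or without TXA will be reported", by provider and by patient rating. It names no test.

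Section 2.1 hypothesises that TXA will "decrease subjective bruising when compared to the control breasts". Section 2.2 mentions bruising in its text, but its table of primary endpoints holds only hematoma and seroma. Section 2.3 and Section 3.1 both place bruising among the secondary outcomes.

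**The concern.** When one rating says which breast is worse, the two treatment counts compete for the same patients: each patient added to the TXA-worse count is lost to the saline-worse count. A two-group chi-squared assumes that the counts are independent. It therefore understates the variance of their difference and gives p-values that are too small.

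This runs against the usual effect of ignoring pairing. For an outcome that tends to occur in both breasts of the same patient, an unpaired test loses precision and errs on the cautious side. For worse-side bruising the dependence is negative by construction, so that defence is not available. At stake is a claim of benefit or harm on a named hypothesis that chance alone would produce more often than 5% of the time.

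**Working it through.** **Inputs.** Section 3.2: "minimum goal of 150 patients (150 breasts will receive TXA, 150 breasts will receive saline", and alpha 0.05. Sidedness is not stated; two-sided is assumed. The share of patients rated equal on both sides, t, is given nowhere and is varied below. The figures are for one rater at one visit.

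**The plan's own figure.** Section 3.2 gives no size or power for bruising. Its one calculation is for hematoma, 5% against 0%: "at least 150 per group to be adequately powered to detect that difference (alpha 0.05, beta 0.2". The two-sided, uncorrected, independent-groups formula gives n = [1.96 × √(2 × 0.025 × 0.975) + 0.8416 × √(0.05 × 0.95)]² / 0.05² = (0.4328 + 0.1834)² / 0.0025 ≈ 152 per group. That reproduces the stated 150 within rounding. With continuity correction the figure would be 190. The planning figure thus fits an uncorrected comparison of independent groups.

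**Variance.** Let q = 1 − t be the share with a worse side, a the number with TXA worse and b the number with saline worse. With no effect, each has probability q/2.

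- True variance of (a − b)/n: [2 × (q/2)(1 − q/2) + 2 × (q/2)²]/n = q/n.
- Variance the two-group chi-squared assumes: 2 × (q/2)(1 − q/2)/n = q(1 − q/2)/n.
- Ratio, true to assumed: 1/(1 − q/2) = 2/(1 + t). This is 2 with no ties, 1.33 at 50% ties and 1.05 at 90%.

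**Approximate size.** 2 × [1 − Φ(1.96 × √(1 − q/2))]. With no ties, 1.96 × 0.707 = 1.386, giving 16.6%. At 50% ties, 1.96 × 0.866 = 1.697, giving 9.0%.

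**Exact size, n = 150.** All outcomes (a, b, ties) are enumerated and the probabilities of the rejected ones summed.

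| Ties | Approximate | Chi-squared, exact | With Yates, exact | McNemar, exact |
|---|---|---|---|---|
| 0% | 16.6% | 16.5% | 16.5% | 4.1% |
| 20% | 12.9% | 13.2% | 11.0% | 4.9% |
| 50% | 9.0% | 9.0% | 7.0% | 5.1% |
| 70% | 7.1% | 7.0% | 5.0% | 4.9% |
| 90% | 5.6% | 5.4% | 2.8% | 4.7% |

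The counts are discrete, so the exact column is not perfectly smooth; at 5% ties it is 16.7%. The exact sign test has size 4.1%, 4.0% and 3.8% at 0%, 20% and 50% ties, and by construction it cannot exceed 5%.

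**One data set.** No ties, saline worse in 84 patients, TXA worse in 66. Chi-squared = 300 × (84² − 66²)² / 150⁴ = 300 × 2700² / 150⁴ = 4.32, p = 0.038. With Yates, 300 × (2700 − 150)² / 150⁴ = 3.85, p = 0.0496. The exact sign test gives p = 0.165. At 83 to 67 neither chi-squared version rejects (3.41 and 3.00). Both therefore reject from 84 to 66 onwards, which is why both have size 16.5% with no ties.

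**The case against.** The strongest reply is that the plan never assigns the chi-squared to bruising. The outcomes listed just before that rule are hematoma, seroma, infection, return to the operating room, aspiration and drain placement. Ecchymosis has its own sentence, and that sentence is descriptive. This stands: a reader might infer that the trial will test bruising at a 9% to 16% error rate, and the documents do not support that. The chi-squared is one plausible reading. The other reading does not clear the plan, because it leaves the hypothesis in Section 2.1 untested.

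Second, a chi-squared need not be the harmful one. A one-sample chi-squared of 50:50 among patients with a difference suits the recorded value and holds 4.1% to 5.2% across the tie shares checked. That is true, but Section 7.1 describes a comparison of two sets of breasts and mentions no one-sample version.

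Third, the inflation depends on ties. With many ties it is small, and with Yates correction it is gone from about 70% ties. This also stands, and it is why the whole range is shown.

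Fourth, a reader might infer that bruising severity is not captured at all, since the Abstract speaks of "rates of seroma, hematoma, severe bruising, and drain output" and a worse-side value cannot yield a severe-bruising rate. Section 9.3 does track ecchymosis of Grade 3 and higher in OnCore, graded by CTCAE (Section 9.2.1). What remains is narrower: no side is stated for those records.

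**Conclusion.** The point holds in conditional form. Either Section 7.1 applies a two-group chi-squared to worse-side bruising, and its nominal 5% test has a true size between 5.4% (90% ties) and about 16.5% (no ties) at 150 patients, or it gives the bruising hypothesis no test. As multiples of 5%, the uncorrected sizes are 1.1 at 90% ties, 1.8 at 50% and 3.3 with none.

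The figures assume a two-sided test, one rater, one visit and no true difference between sides. Section 7.1 has two raters, and Sections 2.3 and 6.3 have several visits whose number varies by patient. No rule combines them, so testing each would add further chances of a false positive.

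This should be fixed, but it does not threaten the trial's main result. A reader might take it as a flaw in the primary analysis; bruising is secondary in Sections 2.3 and 3.1, and the hematoma comparison and its sample size are not affected by this point.

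**What to change.** In Section 7.1, replace the ecchymosis sentence with a paragraph that states:

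- The two-group chi-squared does not apply to bruising.
- Each rating is right worse, left worse or no difference, decoded after blinded rating into TXA side worse, saline side worse or no difference.
- The test is an exact sign test of 50:50 among patients with a difference (McNemar's test is the large-sample equivalent). The share with the saline side worse is reported with its 95% interval, together with the number of ties.
- One visit and one rater form the main bruising analysis. A visit in the 1–4 week window of Section 6.1 would fit the 30-day time frame in Section 2.3. Other visits and the other rater are supportive.
- The 50:50 null assumes that the side given TXA is unrelated to bruising. The document describes no randomisation of side. Section 6.3 puts TXA in the right pocket for every patient, while the calendar in Section 6.1, as it reads here, marks the left breast. These passages must be reconciled, and the basis for allocating sides stated.

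For the Abstract's severe-bruising aim, either record the side with each Grade 3 or higher ecchymosis entry or align the wording with what is measured.

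The cost is one paragraph and, if the visit form lacks it, one extra tick-box. The form is not in the documents. No patients are added. The bruising result becomes harder to declare significant: with no ties, the exact sign test needs a split of 88 to 62 (p = 0.041) where the chi-squared needs 84 to 66. The change should be settled before any sides are decoded, with a stated rule for ratings already taken without a no-difference option.
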